8.4 Ethical Conduct of the Study.....	49
9 MANAGEMENT AND REPORTING OF ADVERSE EVENTS/ADVERSE REACTIONS	50
10 PLANS FOR DISSEMINATING AND COMMUNICATING STUDY RESULTS	51
11. REFERENCES	52
12. LIST OF TABLES	53
13. LIST OF FIGURES	53
ANNEX 1. LIST OF STAND ALONE DOCUMENTS	53
ANNEX 2. ENCEPP CHECKLIST FOR STUDY PROTOCOLS	53

PFIZER CONFIDENTIAL

LIST OF ABBREVIATIONS

Abbreviation	Definition
ARB	Angiotensin II receptor blockers
ACE	Angiotensin-converting-enzyme inhibitor
AE	Adverse event
AEM	Adverse event monitoring
AIDS	Acquired Immune Deficiency Syndrome
AF	Atrial fibrillation
ANOVA	Analysis of variance
ATC	Anatomical Therapeutic Chemical
CHA ₂ DS ₂ -VASc	C: Congestive heart failure
	H: Hypertension
	A: Age \geq 75 years
	D: Diabetes mellitus
	S ₂ : Prior Stroke or transient ischemic attack or Thromboembolism
	V: Vascular disease (peripheral artery disease, myocardial infarction, aortic plaque)
	A: Age 65–74 years
	Sc: Sex category (female sex)
CHADS ₂	C: Congestive heart failure
	H: Hypertension
	A: Age \geq 75 years
	D: Diabetes mellitus
	S ₂ : Prior Stroke or transient ischemic attack or Thromboembolism
COPD	Chronic obstructive pulmonary disease
ECR	Electronic Case Report
GEP	Good Epidemiological Practice
GPP	Good Pharmacoepidemiology Practices
HAS-BLED	H: Hypertension
	A: Abnormal renal and liver function
	S: Stroke
	B: Bleeding
	L: Labile INR
	E: Elderly
	D: Drugs or alcohol
HMO	Health Maintenance Organizations
ICD-10	10th revision of the International classification of diseases
IEA	International Epidemiological Association
IEC	Independent Ethics Committee
INR	International normalized ratio
IRB	Institutional Review Board
ISPE	International Society for Pharmacoepidemiology
ISPOR	International Society for Pharmacoeconomics and Outcomes Research
MANOVA	Multivariate analysis of variance
NI	Non- interventional
NIS	Non-interventional study
NOAC	New oral anticoagulant
NSAID	Non-steroidal anti-inflammatory drugs
NVAF	Non-valvular atrial fibrillation

PFIZER CONFIDENTIAL

Apixaban
B0661148- NON-INTERVENTIONAL STUDY PROTOCOL
Final, 10 October 2019

Abbreviation	Definition
OAC	Oral anticoagulant
SAMe-TT ₂ R ₂	S: Sex (female)
	A: Age (<60 years)
	Me: Medical history
	T: Treatment
	T: Tobacco use (within 2 years)
	R: Race (non-Caucasian)
SPSS	Statistical Package for the Social Sciences
TIA	Transient ischaemic attack
VKA	Vitamin K Antagonist
VTE	Venous thromboembolism

PFIZER CONFIDENTIAL

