5. RATIONALE AND BACKGROUND

Non-valvular atrial fibrillation (NVAF) is an acute or chronic heart disorder that is associated with an increase in the mortality rate, strokes and other thromboembolic events (1). This is further increased by individual conditions of patients, such as hypertension, abnormal renal or hepatic function, stroke, history of or predisposition to bleeding, people over 65, among others. (2)

One of the standard treatments for management of these patients is usually vitamin K antagonists (VKA, for example, warfarin); in the analysis of net clinical benefits of this therapy it is suggested that the effect of VKA is even more positive in patients with a high score on the HAS-BLED (hypertension, abnormal renal/liver function, stroke, bleeding history or predisposition, labile International Normalized Ratio, elderly, drugs/alcohol concomitantly) scale. (3) Another therapeutic alternative is the new oral anticoagulants (NOAC) — dabigatran, rivaroxaban and apixaban —, which according to evidence have advantages in efficacy and safety compared to warfarin (4) and even when the risk of bleeding and stroke are high, the net clinical benefit appears to be greater when compared to warfarin. (5) Likewise, there is a lower prevalence of intracranial hemorrhage and its different subtypes of patients being treated with new oral anticoagulants when compared to warfarin. (6)

While it is true there are several studies that seek to understand the characteristics of patients who were diagnosed with NVAF under different treatment options, and even subpopulation analyses, the evidence at the national level is limited, both in demographic and clinical characteristics and in treatment patterns of this population. In a retrospective descriptive study of an emergency department in a third level care center in the city of Bogota, it was observed that the main comorbidities of patients with atrial fibrillation (AF) were arterial hypertension and heart failure where most patients do not receive anticoagulation. (7) In turn, for the overall population it is estimated that the prevalence of AF in Colombia (4.8%) seems to be higher than that reported in developed countries (0.03% to 1.25%) (8), according to a study conducted in a university hospital in the country (9).

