I130	Hypertensive heart and renal disease with (congestive) heart failure
I132	Hypertensive heart and renal disease with both (congestive) heart failure and renal failure
I110	Hypertensive heart disease with (congestive) heart failure

- *Peripheral vascular disease*

ICD-10	Description
I70	Atherosclerosis
I71	Aortic aneurysm and dissection
I731	Thromboangiitis obliterans [Buerger]
I738	Other specified peripheral vascular diseases
I739	Peripheral vascular disease, unspecified

PFIZER CONFIDENTIAL

ICD-10	Description
I771	Stricture of artery
I790	Aneurysm of aorta in diseases classified elsewhere
I792	Peripheral angiopathy in diseases classified elsewhere
K551	Chronic vascular disorders of intestine
K558	Other vascular disorders of intestine
K559	Vascular disorder of intestine, unspecified
Z958	Presence of other cardiac and vascular implants and grafts
Z959	Presence of cardiac and vascular implant and graft, unspecified

▪ *Dementia*

ICD-10	Description
F00	Dementia in Alzheimer's disease
F01	Vascular dementia
F02	Dementia in other diseases classified elsewhere
F03	Unspecified dementia
G30	Alzheimer's disease
F051	Delirium superimposed on dementia
G311	Senile degeneration of brain, not elsewhere classified

▪ *Cerebrovascular disease*

ICD-10	Description
G45	Transient cerebral ischaemic attacks and related syndromes
G46	Vascular syndromes of brain in cerebrovascular diseases
I60	Subarachnoid haemorrhage
I61	Intracerebral haemorrhage
I62	Other nontraumatic intracranial haemorrhage
I63	Cerebral infarction
I64	Stroke, not specified as haemorrhage or infarction
I65	Occlusion and stenosis of precerebral arteries, not resulting in cerebral infarction
I66	Occlusion and stenosis of cerebral arteries, not resulting in cerebral infarction
I67	Other cerebrovascular diseases
I68	Cerebrovascular disorders in diseases classified elsewhere
I69	Sequelae of cerebrovascular disease
H340	Transient retinal artery occlusion

▪ *Chronic pulmonary disease*

ICD-10	Description
J40	Bronchitis, not specified as acute or chronic
J41	Simple and mucopurulent chronic bronchitis
J42	Unspecified chronic bronchitis
J43	Emphysema
J44	Other chronic obstructive pulmonary disease
J45	Asthma
J46	Status asthmaticus
J47	Bronchiectasis
J60	Coalworker's pneumoconiosis
J61	Pneumoconiosis due to asbestos and other mineral fibres
J62	Pneumoconiosis due to dust containing silica

PFIZER CONFIDENTIAL

ICD-10	Description
J63	Pneumoconiosis due to other inorganic dusts
J64	Unspecified pneumoconiosis

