C84	Peripheral and cutaneous T-cell lymphomas
C85	Other and unspecified types of non-Hodgkin's lymphoma
C88	Malignant immunoproliferative diseases
C90	Multiple myeloma and malignant plasma cell neoplasms
C91	Lymphoid leukaemia
C92	Myeloid leukaemia
C93	Monocytic leukaemia
C94	Other leukaemias of specified cell type
C95	Leukaemia of unspecified cell type
C96	Other and unspecified malignant neoplasms of lymphoid, haematopoietic and related tissue
C97	Malignant neoplasms of independent (primary) multiple sites

3 points each:

- *Moderate or severe liver disease*

ICD-10	Description
K704	Alcoholic hepatic failure
K711	Toxic liver disease with hepatic necrosis
K721	Chronic hepatic failure
K729	Hepatic failure, unspecified
K765	Hepatic veno-occlusive disease
K766	Portal hypertension
K767	Hepatorenal syndrome
I850	Oesophageal varices with bleeding
I859	Oesophageal varices without bleeding
I864	Gastric varices
I982	Oesophageal varices in diseases classified elsewhere

6 points each:

- *Metastatic solid tumor*

ICD-10	Description
C77	Secondary and unspecified malignant neoplasm of lymph nodes
C78	Secondary malignant neoplasm of respiratory and digestive organs
C79	Secondary malignant neoplasm of other sites
C80	Malignant neoplasm without specification of site

- *Human immunodeficiency virus (HIV)-AIDS*

ICD-10	Description
B20	Human immunodeficiency virus [HIV] disease resulting in infectious and parasitic diseases
B21	Human immunodeficiency virus [HIV] disease resulting in malignant neoplasms
B22	Human immunodeficiency virus [HIV] disease resulting in other specified diseases
B24	Unspecified human immunodeficiency virus [HIV] disease
Z21	Asymptomatic human immunodeficiency virus [HIV] infection status

One point was added to the total score of the Charlson index for each decade after the age of 50 years:

50 to 59: 1 point,

60 to 69: 2 points,

70 to 79: 3 points,

80 to 89: 4 points,

>90: 5 points.

- **CHA₂DS₂-VACs score:** The CHA₂DS₂-VACs score will be used to analyze the effect of stratification of the risk of stroke. CHA₂DS₂-VACs scores range from 0 to 9. ICD-10 diagnostic codes for each component of the index when applicable:
 - **C:** I11.0, I13.0, I13.2, I50
Score 1 point

ICD-10	Description
I110	Hypertensive heart disease with (congestive) heart failure
I130	Hypertensive heart and renal disease with (congestive) heart failure
I132	Hypertensive heart and renal disease with both (congestive) heart failure and renal failure
I50	Heart failure

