H: I10, I11, I12, I13, I15

Score 1 point

ICD-10	Description
I10	Essential (primary) hypertension
I11	Hypertensive heart disease
I12	Hypertensive renal disease
I13	Hypertensive heart and renal disease
I15	Secondary hypertension

A: Age \geq 75 years

Score 2 points

D: E10 a E14

Score 1 point

ICD-10	Description
E10	Insulin-dependent diabetes mellitus
E11	Non-insulin-dependent diabetes mellitus
E12	Malnutrition-related diabetes mellitus
E13	Other specified diabetes mellitus
E14	Unspecified diabetes mellitus

S2: G45.0, G45.1, G45.2, G45.3, G45.8, G45.9

Score 2 points

ICD-10	Description
G450	Vertebral-basilar artery syndrome
G451	Carotid artery syndrome (hemispheric)
G452	Multiple and bilateral precerebral artery syndromes
G453	Amaurosis fugax
G458	Other transient cerebral ischaemic attacks and related syndromes

V: I26, I82, I21- I25, I65, I70- I72, I73.1, I73.8, I73.9, I79.0, I79.2, K55.1, K55.8, K55.9, Z95.8, Z95.9

Score 1 point

ICD-10	Description
I26	Pulmonary embolism
I82	Other venous embolism and thrombosis
I21	Acute myocardial infarction
I22	Subsequent myocardial infarction
I23	Certain current complications following acute myocardial infarction
I24	Other acute ischaemic heart diseases
I25	Chronic ischaemic heart disease
I65	Occlusion and stenosis of precerebral arteries, not resulting in cerebral infarction
I70	Atherosclerosis
I71	Aortic aneurysm and dissection
I72	Other aneurysm
I731	Thromboangiitis obliterans [Buerger]
I738	Other specified peripheral vascular diseases
I739	Peripheral vascular disease, unspecified
I790	Aneurysm of aorta in diseases classified elsewhere
I792	Peripheral angiopathy in diseases classified elsewhere
K551	Chronic vascular disorders of intestine
K558	Other vascular disorders of intestine

A: Age 64-74 years

Score 1 point

Sc: Sex category (female)

Score 1

- **HASBLED score:** The HAS-BLED score will be used to analyze the risk of bleeding. The modified HAS-BLED score ranges from 0 to 8. ICD-10 diagnostic codes for each component of the index when applicable:

•

H: I10, I11, I12, I13, I15

Score 1 point

ICD-10	Description
I10	Essential (primary) hypertension
I11	Hypertensive heart disease
I12	Hypertensive renal disease
I13	Hypertensive heart and renal disease
I15	Secondary hypertension

Apixaban

B0661148- NON-INTERVENTIONAL STUDY PROTOCOL

Final, 10 October 2019

A: N03.2, N03.3, N03.4, N03.5, N03.6, N03.7, N05.2, N05.3, N05.4, N05.5, N05.6, N057, N18- N19, N25.0, Z49.0, Z49.2, Z94.0, Z99.2

Score 1 point

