Peripheral artery disease	I702 Atherosclerosis of arteries of the extremities I708 Atherosclerosis of other arteries I709 Generalised and unspecified atherosclerosis
Anaemia	D50 Iron deficiency anaemia D51 Vitamin B12 deficiency anaemia D52 Folate deficiency anaemia D53 Other nutritional anaemias D55 Anaemia due to enzyme disorders D56 Thalassaemia D57 Sickle-cell disorders D58 Other hereditary haemolytic anaemias D59 Acquired haemolytic anaemia
Congestive heart failure	I110 Hypertensive heart disease with (congestive) heart failure I130 Hypertensive heart and renal disease with (congestive) heart failure I132 Hypertensive heart and renal disease with both (congestive) heart failure and renal failure
Renal disease	B15 Acute hepatitis A B16 Acute hepatitis B B17 Other acute viral hepatitis B18 Chronic viral hepatitis B19 Unspecified viral hepatitis C22 Malignant neoplasm of liver and intrahepatic bile ducts K70 Alcoholic liver disease K71 Toxic liver disease K72 Hepatic failure, not elsewhere classified K73 Chronic hepatitis, not elsewhere classified K74 Fibrosis and cirrhosis of liver

PFIZER CONFIDENTIAL

Variable	Operacional definition ICD-10
	K75 Other inflammatory liver diseases K76 Other diseases of liver K77 Liver disorders in diseases classified elsewhere Z944 Liver transplant status
Myocardial infarction	I21 Acute myocardial infarction I22 Subsequent myocardial infarction I252 Old myocardial infarction
Peripheral vascular disease	I70 Atherosclerosis I71 Aortic aneurysm and dissection I731 Thromboangiitis obliterans [Buerger] I738 Other specified peripheral vascular diseases I739 Peripheral vascular disease, unspecified I771 Stricture of artery I790 Aneurysm of aorta in diseases classified elsewhere I792 Peripheral angiopathy in diseases classified elsewhere K551 Chronic vascular disorders of intestine K558 Other vascular disorders of intestine K559 Vascular disorder of intestine, unspecified Z958 Presence of other cardiac and vascular implants and grafts Z959 Presence of cardiac and vascular implant and graft, unspecified
TIA	G450 Vertebro-basilar artery syndrome G458 Other transient cerebral ischaemic attacks and related syndromes G451 Carotid artery syndrome (hemispheric) G459 Transient cerebral ischaemic attack, unspecified
Coronary artery disease	I20 Angina pectoris I21 Acute myocardial infarction

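### The Charlson and Table 2 heart-failure code lists omit I50, the Table 2 'Renal disease' row holds only liver codes, and the CHA2DS2-VASc age band differs by a year between sections

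*Combined protocol and SAP*

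**What the plan says.** Section 7.3.1 defines heart failure by ICD-10 code in three places.

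- CHA2DS2-VASc, item C: "I11.0, I13.0, I13.2, I50".
- Charlson index, 1-point items: I110, I130, I132 ("Hypertensive heart and renal disease with both (congestive) heart failure and renal failure"), then I110 a second time. I50 is absent.
- Table 2 (baseline variables or possible confounders): I110, I130, then "I132 Hypertensive heart and renal disease with both (congestive) heart failure and renal failure". I50 is absent.

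The Table 2 row labelled 'Renal disease' begins "B15 Acute hepatitis A B16 Acute hepatitis B B17 Other acute viral hepatitis" and continues with B18, B19, C22, K70 to K77 and Z944.

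The second age item of CHA2DS2-VASc is "A: Age 64-74 years" in section 7.3.1 and "A: Age 65–74 years" in the list of abbreviations.

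Table 1 (section 7.3) lists chronic heart failure as a Yes/No variable from the medical record, without codes. It lists moderate renal disease (by creatinine) and severe renal disease (dialysis or transplant) with their own definitions, and has a separate graded liver variable.

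**The concern.** By their printed descriptions, the codes in the short lists cover only hypertensive heart disease, or hypertensive heart and renal disease, with failure. A patient coded I50 and none of those three has heart failure for CHA2DS2-VASc but not for Charlson or Table 2. The same person is classified two ways within one dataset.

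The first primary objective (section 6) is to describe demographic and clinical characteristics. Section 5 cites a series from one Bogota emergency department in which the "main comorbidities of patients with atrial fibrillation (AF) were arterial hypertension and heart failure". An undercount of heart failure would therefore affect a comorbidity that the plan itself treats as prominent. A row labelled renal but filled with hepatic codes would put the wrong disease under that label in any table built from it.

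**Working it through.** **1. Heart-failure lists compared as sets.**

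- CHA2DS2-VASc item C = {I110, I130, I132, I50}.
- Table 2 = {I110, I130, I132}. Item C minus Table 2 = {I50}.
- Charlson = {I110, I130, I132}, with I110 printed twice. Item C minus Charlson = {I50}.

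Adding I50 makes all three lists identical.

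**2. Renal lists compared as sets.**

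- Table 2 'Renal disease': 15 entries (B15-B19, C22, K70-K77, Z944). All are viral hepatitis, liver cancer, other liver disease or liver transplant.
- Charlson moderate or severe renal disease: 22 codes, all kidney-related. Overlap with the Table 2 row: 0.
- HAS-BLED renal item: 19 codes, all kidney-related. Overlap with the Table 2 row: 0.

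Table 2 has no row labelled liver disease and no row of kidney codes.

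**3. Age item.** A patient aged 64 scores 1 point under section 7.3.1 and 0 under the abbreviations. The documents give no age distribution, so the number affected cannot be stated.

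**4. Possible size of the heart-failure effect.** The plan has no figure to reproduce. Let p be the true heart-failure prevalence and s the share of heart-failure patients coded only I50. Neither is in the documents; the ranges below are assumptions. N = 7,500 is the patient count in section 7.5.

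- Patients missed = N × p × s
- Prevalence reported, if Table 2 codes decide = p × (1 − s)
- Shortfall in mean Charlson = p × s × 1 point

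| p | s | Missed | Reported prevalence | Mean Charlson shortfall |
|---|---|---|---|---|
| 20% | 25% | 7,500 × 0.20 × 0.25 = 375 | 15% | 0.05 |
| 20% | 95% | 7,500 × 0.20 × 0.95 = 1,425 | 1% | 0.19 |
| 40% | 25% | 7,500 × 0.40 × 0.25 = 750 | 30% | 0.10 |
| 40% | 95% | 7,500 × 0.40 × 0.95 = 2,850 | 2% | 0.38 |

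The Charlson column follows from the Charlson list itself. The prevalence column applies only if Table 2 decides the Yes/No variable. The direction, understatement, does not depend on the assumed values.

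**The case against.** The strongest reply is that Table 1 is the variable table. It takes clinical characteristics from the medical record, section 7.4.2 says the record characterises patients at baseline, and section 7.6.1 has trained physicians abstract it. Nothing says that Table 2 codes override a physician's reading of the chart. A reader might infer that two characteristics in the primary objective are certain to be wrong; the documents do not support that. For heart failure the matter is open, because Table 2 is headed as an ICD-10 operational definition and section 7.3.1 applies ICD lists to other variables taken from the medical record, such as haemorrhagic stroke.

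For renal disease the reply largely succeeds. The Table 1 renal variables have their own definitions, and the Charlson and HAS-BLED renal items use kidney codes. It would be wrong to infer that the study cannot identify renal patients. Section 7.7 specifies no adjusted model and rules out treatment comparison, so no stated analysis would be biased by a miscoded confounder.

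Three further cautions stand.

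- The repeated I110 might suggest that it displaced I50. That is weak evidence, since several other Charlson lists are printed twice in full.
- A reader might assume that nearly all heart failure is coded I50 and that reported prevalence would fall to a few percent. The documents give no coding share, so only a wide range is defensible.
- A lost row or label in the Table 2 text cannot be fully excluded. The table breaks across pages inside the renal row, but the codes on both sides of the break are hepatic, so the break alone does not explain the mismatch. The sponsor can check the source at once.

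Validating the case report on 30 records (section 7.6.1) may expose such problems, but it does not correct the written lists.

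**Conclusion.** The code-list defects are confirmed on the printed text. They support four conclusions of differing strength.

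- **Charlson:** wrong as written. Each patient with heart failure coded only I50 scores one point too low.
- **Heart-failure prevalence:** understated only if Table 2 codes decide the variable, which the protocol leaves unsaid.
- **Renal disease:** the error is confined to the Table 2 covariate, which would report liver disease as renal disease.
- **CHA2DS2-VASc:** heart failure is coded with I50 there and is unaffected, but each patient aged 64 gains a point under section 7.3.1.

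Under the assumed ranges (p of 20-40%, s of 25-95%), 375 to 2,850 of 7,500 patients would be missed and mean Charlson would be 0.05 to 0.38 too low. Confidence is high in the mismatches and low in these magnitudes.

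**What to change.** 1. Use the four-code list (I11.0, I13.0, I13.2, I50) for heart failure in the Charlson index and in Table 2.
2. Relabel the hepatic row of Table 2 'Liver disease', and add a 'Renal disease' row built from the protocol's own renal codes. State which list is used: the Charlson and HAS-BLED renal lists differ, with I120, I131 and Z491 only in Charlson.
3. Change the second CHA2DS2-VASc age item in section 7.3.1 from 64-74 to 65-74.
4. State for each baseline characteristic whether Table 1 chart abstraction or the Table 2 codes govern. Say the same for the SAMe-TT2R2 history item, which uses heart failure, hepatic and renal disease but gives no codes for them.

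The cost is a few edits to code lists and one added statement, with no new data. The protocol is dated 10 October 2019 and data collection is planned from 15 November 2019, so the edits fit before abstraction. Correcting later could mean re-deriving variables or reopening charts.

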Leukemia	Clinical characteristic	Medical record	Yes, No

PFIZER CONFIDENTIAL

Variable	Role	Data source (s)	Operational definition
Malignant lymphoma	Clinical characteristic	Medical record	Yes, No
Peptic ulcer disease	Clinical characteristic	Medical record	Yes, No
Metastatic solid tumor	Clinical characteristic	Medical record	Yes, No
History of ischemic or hemorrhagic stroke	Clinical characteristic	Medical record	Yes, No
History of TIA	Clinical characteristic	Medical record	Yes, No
History of de tromboembolismo	Clinical characteristic	Medical record	Yes, No
Enfermedad coronaria	Clinical characteristic	Medical record	Yes, No
History of de hemorragia gastrointestinal	Clinical characteristic	Medical record	Yes, No
History of Intracranial bleeding	Clinical characteristic	Medical record	Yes, No
History of Other bleeding	Clinical characteristic	Medical record	Yes, No
Bleeding history or predisposition at start OAC treatment	Clinical characteristic	Medical record	Yes, No
INR > 60% at start OAC treatment	Clinical characteristic	Medical record	Yes, No
Use of aspirin at start OAC treatment	Clinical characteristic	Medical record	Yes, No
Use of clopidogrel at start OAC treatment	Clinical characteristic	Medical record	Yes, No
Use of NSAIDs at start OAC treatment	Clinical characteristic	Medical record	Yes, No
HASBLED at start OAC treatment	Clinical characteristic	Medical record	Score – number higher than 0
CHA2DS2-VASc at start OAC treatment	Clinical characteristic	Medical record	Score – number higher than 0
Anaemia at start OAC treatment	Clinical characteristic	Medical record	Yes, No
Stroke	Clinical outcome	Medical record	Yes, No
Time to stroke	Clinical outcome	Medical record	Date of event dd/mm/yy

Pfizer Confidential

Variable	Role	Data source (s)	Operational definition
Type of stroke	Clinical outcome	Medical record	Ischemic stroke, Haemorrhagic or not specified
Pulmonary embolism	Clinical outcome	Medical record	Yes, No
Time to pulmonary embolism	Clinical outcome	Medical record	Date of event dd/mm/yy
Gastrointestinal bleeding	Clinical outcome	Medical record	Yes, No
Time to gastrointestinal bleeding	Clinical outcome	Medical record	Date of event dd/mm/yy
Intracranial bleeding	Clinical outcome	Medical record	Yes, No
Time to Intracranial bleeding	Clinical outcome	Medical record	Date of event dd/mm/yy
Other major bleeding	Clinical outcome	Medical record	Yes, No
Time to other major bleeding	Clinical outcome	Medical record	Date of event dd/mm/yy
CCI			

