Z714	Alcohol abuse counselling and surveillance
Z721	Alcohol use

Codes Anatomical Therapeutic Chemical (ATC): B01AC, M01A

- SMAe-TT₂R₂ score:** The estimation of SAMe-TT₂R₂ will be performed by adding the following variables:

Sex (female) Score 1 point

Age (<60 years) Score 1 point

Medical history (history of more than two of the following: hypertension, diabetes, coronary artery disease or myocardial infarctions, peripheral artery disease, heart failure, stroke; pulmonary, hepatic, or renal disease) Score 1 point

Treatment (interacting medications , amiodarone ATC- C01BD01) Score 1 point

Tobacco use (within 2 years) Score 2 points

PFIZER CONFIDENTIAL

Race (non-Caucasian) Score 2 points

Table 2. Baseline variables or possible confounders

Variable	Operacional definition ICD-10
Diabetes	E10 Insulin-dependent diabetes mellitus E11 Non-insulin-dependent diabetes mellitus E12 Malnutrition-related diabetes mellitus E13 Other specified diabetes mellitus E14 Unspecified diabetes mellitus
Hypertension	I10 Essential (primary) hypertension I11 Hypertensive heart disease I12 Hypertensive renal disease I13 Hypertensive heart and renal disease I15 Secondary hypertension
Ischaemic stroke	I63 Cerebral infarction Excepto I636 Cerebral infarction due to cerebral venous thrombosis, nonpyogenic I64 Stroke, not specified as haemorrhage or infarctionz
Haemorrhagic stroke	I60 Subarachnoid haemorrhage I61 Intracerebral haemorrhage I62 Other nontraumatic intracranial haemorrhage

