Bleeding (gastrointestinal, intracranial, other)	I60 Subarachnoid haemorrhage I61 Intracerebral haemorrhage I62 Other nontraumatic intracranial haemorrhage S064 Epidural haemorrhage S065 Traumatic subdural haemorrhage S066 Traumatic subarachnoid haemorrhage I850 Oesophageal varices with bleeding K250 Acute with haemorrhage K252 Acute with both haemorrhage and perforation K254 Chronic or unspecified with haemorrhage K256 Chronic or unspecified with both haemorrhage and perforation K260 Acute with haemorrhage K262 Acute with both haemorrhage and perforation K264 Chronic or unspecified with haemorrhage K266 Chronic or unspecified with both haemorrhage and perforation K270 Acute with haemorrhage K272 Acute with both haemorrhage and perforation K274 Chronic or unspecified with haemorrhage K276 Chronic or unspecified with both haemorrhage and perforation K280 Acute with haemorrhage K282 Acute with both haemorrhage and perforation K284 Chronic or unspecified with haemorrhage K286 Chronic or unspecified with both haemorrhage and perforation K290 Acute haemorrhagic gastritis K625 Haemorrhage of anus and rectum K920 Haematemesis K921 Melaena K922 Gastro-intestinal haemorrhage, unspecified D62 Acute posthaemorrhagic anaemia H356 Retinal haemorrhage H431 Vitreous haemorrhage H450 Vitreous haemorrhage in diseases classified elsewhere H922 Otorrhagia

PFIZER CONFIDENTIAL

Variable	Operacional definition ICD-10
	I312 Haemopericardium, not elsewhere classified J942 Haemothorax R04 Haemorrhage from respiratory passages K661 Haemoperitoneum M250 Haemarthrosis N02 Recurrent and persistent haematuria N938 Other specified abnormal uterine and vaginal bleeding N939 Abnormal uterine and vaginal bleeding, unspecified N950 Postmenopausal bleeding R31 Unspecified haematuria R58 Haemorrhage, not elsewhere classified T792 Traumatic secondary and recurrent haemorrhage
Systemic embolism	I74 Arterial embolism and thrombosis
Alcohol consumption	E244 Alcohol-induced pseudo-Cushing's syndrome E52 Niacin deficiency [pellagra] G312 Degeneration of nervous system due to alcohol G621 Alcoholic polyneuropathy G721 Alcoholic myopathy I426 Alcoholic cardiomyopathy K292 Alcoholic gastritis K70 Alcoholic liver disease K860 Alcohol-induced chronic pancreatitis O354 Maternal care for (suspected) damage to foetus from alcohol T51 Toxic effect of alcohol Z714 Alcohol abuse counselling and surveillance Z721 Alcohol use

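### The Table 2 code list for coronary artery disease stops at I20 and I21, out of step with the ischaemic codes the protocol uses elsewhere

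*Combined protocol and SAP*

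**What the plan says.** Table 2, at the end of section 7.3.1, gives ICD-10 operational definitions for baseline variables and possible confounders. Its last row, coronary artery disease, lists "I20 Angina pectoris I21 Acute myocardial infarction" and nothing more. A few rows above, myocardial infarction is defined by "I21 Acute myocardial infarction I22 Subsequent myocardial infarction I252 Old myocardial infarction".

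The CHA2DS2-VASc definition in section 7.3.1 scores vascular disease from its own list, which begins "V: I26, I82, I21- I25, I65". The table beneath it labels I25 as chronic ischaemic heart disease.

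Table 1 (section 7.3) carries the variable as "Enfermedad coronaria", a Yes/No clinical characteristic taken from the medical record, with no codes. Section 7.4.2 names the medical record as the source of baseline characteristics. The SAMe-TT2R2 history item counts "coronary artery disease or myocardial infarctions" as one condition among several.

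For TIA, Table 2 lists G45.0, G45.1, G45.8 and G45.9. The S2 line of CHA2DS2-VASc lists those four plus G45.2 and G45.3.

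**The concern.** The first primary objective is to describe the clinical characteristics of the cohort, and coronary disease is one of them. A list that holds angina and acute infarction but not chronic ischaemic heart disease or old infarction does not describe the condition as the protocol treats it elsewhere.

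Two things are at stake. The reported prevalence of coronary disease would be too low. The baseline table could also contradict itself, because a patient with an old infarction would appear in the infarction row and be absent from the coronary disease row.

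**Working it through.** The plan states no coronary disease prevalence, so there is no figure to reproduce. The check compares the code lists.

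**Inputs**
- Coronary artery disease, Table 2: {I20, I21}
- Vascular item, CHA2DS2-VASc, ischaemic heart part: {I21, I22, I23, I24, I25}
- Myocardial infarction, Table 2: {I21, I22, I25.2}
- Pre-index exclusion codes, section 7.2.2: include I22 but not I23, I24 or I25

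**Step 1. Codes scored in the vascular item but absent from the coronary row:** {I22, I23, I24, I25}.

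**Step 2. Remove codes that cannot occur at baseline.** A prior I22 is an exclusion in 7.2.2, which leaves {I23, I24, I25}. The omission of I22 therefore has essentially no effect.

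**Step 3. How patients would be classified if the lists are applied literally**

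| Only ischaemic code recorded | Infarction row | Coronary row | Vascular item |
|---|---|---|---|
| I25.2 | Yes | No | scored |
| I25 other than I25.2 | No | No | scored |
| I23 or I24 | No | No | scored |

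The first line is a contradiction inside one table and needs no assumption about prevalence.

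**Step 4. The abstract.** Its exclusion list also contains I21, which 7.2.2 does not. If the abstract's list governed, only I20 in the coronary row could occur before the index date. The two exclusion lists need reconciling in any case.

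**Step 5. Illustration of size, on assumptions only.** Let p be the true prevalence of coronary disease and s the share of those patients who have neither I20 nor I21. Neither is in the documents. Observed prevalence = p × (1 − s), and patients missed = 7,500 × p × s. The 7,500 is the count in section 7.5; the number analysed also depends on the exclusions and on chart access.

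| p | s = 10% | s = 75% |
|---|---|---|
| 10% | 9.0% observed, 75 missed | 2.5% observed, about 562 missed |
| 20% | 18% observed, 150 missed | 5% observed, 1,125 missed |
| 30% | 27% observed, 225 missed | 7.5% observed, about 1,688 missed |

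The understatement, p × s, runs from 0.10 × 0.10 = 1 percentage point to 0.30 × 0.75 = 22.5 points. The width of that range reflects the assumptions. If physicians record coronary disease directly from the chart, whatever the code, s is close to zero and so is the bias.

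**Step 6. Downstream scores.** CHA2DS2-VASc uses its own list, so it does not change. SAMe-TT2R2 counts coronary disease or infarction as one condition, so I25.2 is already caught through infarction. Only I23, I24 and the rest of I25 could be missed there. The point requires more than two conditions, so a missed one matters only when it decides whether that threshold is passed.

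**Step 7. TIA.** S2 minus the Table 2 row = {G45.2, G45.3}. The effect is likely to be small.

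**The case against.** **The row may be incomplete in the text supplied.** It is the last row of a table that starts on page 41, and section 7.4 starts on page 44. The final fragment of the table holds 26 code lines against 52 on the page before. Other code tables also stop short of their own header lines: the S2 table, for example, ends before G45.9. This stands, and the source page has to be checked. It explains less well the mismatches in rows that are followed by others. The TIA row is one. The heart failure row, which lacks the I50 scored by CHA2DS2-VASc item C, is another.

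**The variable comes from chart review.** Table 1 and section 7.4.2 say so, and section 7.6.1 has trained physicians abstract it on a form validated for alternative codings. A reader might infer from the short list that reported coronary disease will certainly be far too low. The documents do not support that, because they do not establish that codes alone decide the variable. But Table 2 is the only definition given, section 7.6.1 ties the variables to the protocol, and nothing says that clinical judgement overrides the list. The risk remains until that is written down.

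**The vascular item is a different concept.** It includes I26 and I65, so a vascular point without coronary disease is not in itself a contradiction. This is correct. The conflict between the infarction and coronary rows does not depend on it.

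**Little else depends on the variable.** Section 7.7 specifies no adjusted model using it and rules out treatment comparison. This also stands, and limits the consequence to the descriptive tables and a small part of SAMe-TT2R2.

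A reader might also see the same fault in the anaemia row, which ends at "D58 Other hereditary haemolytic anaemias D59 Acquired haemolytic anaemia" although "D62 Acute posthaemorrhagic anaemia" appears elsewhere in Table 2. That code is already captured in the baseline bleeding row. Keeping it there is a defensible separation, so extending the anaemia list is a preference.

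**Conclusion.** The inconsistency holds on the text supplied. If the Table 2 list is applied, patients with only I23, I24 or I25 are recorded as free of coronary disease, and patients with only I25.2 are recorded inconsistently within one table. Prevalence would be understated by an amount that the documents do not let us quantify, and by less if chart abstraction overrides the list. The percentages in the illustration are assumptions and should not be cited as an estimate.

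This rests on the row being complete in the source document and on the list being used to classify patients. It is worth correcting because it touches a primary-objective variable and costs little. It does not threaten the study: no treatment comparison depends on it, CHA2DS2-VASc is unaffected, and the possible effect on SAMe-TT2R2 is narrow.

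**What to change.** 1. Check the source page of Table 2 to confirm that the coronary artery disease row ends at I21.
2. If it does, set the row to I20-I25 and apply that list in the chart abstraction. State in Table 1 or section 7.6.1 how the code list and the physician's reading of the chart combine.
3. Use one TIA list, G45.0-G45.3, G45.8 and G45.9, in both Table 2 and item S2.

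The cost is a code-list edit and a line in the abstraction instructions, with no new data source. It is cheapest before abstraction starts. Table 1 records coronary disease only as Yes or No, so a later correction could mean returning to the charts.
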